Safety follow-up visits should be conducted 30, 60, 90 days after the last dose of study treatment. Safety follow-up period refers to the 90 days after the last dose of the investigational treatment or the start of new anti-cancer treatment, whichever occurs earlier. Survival follow-up should be conducted every 12 weeks after the last dose of study treatment. Apart from subjects who discontinue treatment due to disease progression assessed by tumor imaging, radiological assessment should be performed at scheduled time points until radiological disease progression, the start of new anti-cancer treatment, death, or the end of this trial, whichever occurs first.

Key Inclusion/Exclusion Criteria:

Inclusion Criteria:

- 1. Subjects who are willing to participate in this trial; fully understand and are fully informed of this trial, and are able to provide written informed consent form (ICF); are willing and able to follow all study procedures.
- 2. Subjects are ≥ 18 years and ≤ 75 years of age on the day of signing informed consent.
- 3. Subjects must have a histologically confirmed ENKTL at the study site. Both nasal and non-nasal ENKTL are allowed.
- 4. Subjects must have relapsed or refractory ENKTL failing asparaginase-based chemotherapy or chemoradiotherapy. (Relapse: disease progression after response to the last treatment; refractory: no response to the last treatment.)
- 5. ECOG PS of 0 or 1.
- 6. Life expectancy ≥ 12 weeks.
- 7. Subjects must have at least one evaluable or measurable lesion per Lugano 2014 classification [An evaluable lesion is a lymph node or extranodal lesion with radioactive uptake higher than liver on ¹⁸F-Fluorodeoxyglucose/ Positron Emission Tomography (¹⁸FDG/PET) and with typical lymphoma characteristics on PET and (or) computed tomography (CT); Measurable lesion: the longest diameter (LDi) is of > 15 mm for nodal lesion or >10 mm for extranodal lesion (if the only measurable lesion has received prior radiotherapy, the subject must have evidence of radiological progression after radiotherapy), and concurrent elevated uptake of ¹⁸FDG]. Absence of measurable lesion with diffuse ¹⁸FDG uptake increase in the liver should be ruled out first.
- 8. Subjects must provide stained tumor tissue sections and corresponding pathological reports or unstained tumor tissue sections (or tissue block) for central pathology review. Investigators may enroll subjects before the result of central pathology review.

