- 9. Subjects must have adequate organ function and bone marrow function without severe hematopoietic disorder, or heart, lung, liver or kidney dysfunction or immune deficiency (no blood transfusion, granulocyte colony-stimulating factor or other relevant medical supporting care within 14 days before the first dose of study treatment):
 - a) Absolute neutrophil count $\geq 1.0 \times 10^9 / L$;
 - b) Platelets $\geq 50 \times 10^9$ /L;
 - c) Hemoglobin $\ge 8 \text{ g/dL};$
 - d) Creatinine clearance \geq 40 mL/min (according to Cockcroft-Gault equation);
 - e) Serum total bilirubin \le 1.5 \times ULN, unless considered to be due to Gilbert's disease, where it must be \le 3 \times ULN
 - f) Aspartate aminotransferase (AST) or alanine aminotransferase (ALT) $\leq 2.5 \times ULN$;
 - g) Coagulation: International normalized ratio (INR) $\leq 1.5 \times$ ULN; prothrombin time (PT) and activated partial thromboplastin time (APTT) $\leq 1.5 \times$ ULN (unless the subject is on anti-coagulant therapy and PT and APTT at screening are within the expected range for patients on anti-coagulant).
- 10. Subjects with prior anti-cancer treatment can only be enrolled when the toxicity of prior anticancer treatment has recovered to baseline or \leq Grade 1 according to Common Terminology Criteria for Adverse Events (CTCAE) v4.03. For patients with irreversible Grade 2 toxicities (e.g. thrombocytopenia, anemia, neurotoxicity, alopecia, and hearing impairment) that is anticipated to be unlikely to worsen during study treatment, the subject can be enrolled after approval by the medical monitor of the sponsor.
- 11. Women of childbearing potential (WOCBP, as defined in Section 4.1.4) must have a negative serum pregnancy test ≤7 days before the first dose of investigational product. WOCBP or fertile

men and their WOCBP partners must agree to use an effective contraceptive method from providing signed ICF through 6 months after the last dose of the investigational product. (Refer to Section 4.1.5 for details.)

Exclusion Criteria:

- 1. Aggressive natural killer-cell leukemia or ENKTL patients who have any degree of leukemic involvement will be excluded.
- 2. Concomitant with hemophagocytic lymphohistiocytosis.
- 3. Current or historical primary central nervous system lymphoma (PCNSL) or secondary CNS involvement.
- 4. Prior allogeneic organ transplantation.

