- 13. Any use of traditional Chinese medicines or herbal preparations with anti-tumor indications within 7 days before the first dose of investigational product.
- 14. Has received a live vaccine within 28 days before the first dose of investigational product. (Attenuated influenza vaccine is allowed).
- 15. Known history of human immunodeficiency virus (HIV) infection and/or acquired immune deficiency syndrome (AIDS).
- 16. Subjects at the active phase of chronic hepatitis B or with active hepatitis C. Subjects who are hepatitis B surface antigen (HBsAg) positive or hepatitis C virus (HCV) antibody-positive at screening must not be enrolled until further definitive testing with hepatitis B virus (HBV) DNA titers (≤ 2500 copies/mL or 500 IU/mL) and HCV RNA tests (≤ the lower limit of detection) can

conclusively rule out the presence of active hepatitis B or C that requires treatment, respectively. Subjects that carry the hepatitis B virus, with stable hepatitis B (HBV DNA titer ≤ 2500 copies/mL or 500 IU/mL) after medical treatment or with cured hepatitis C are permitted to enroll.

- 17. History of interstitial lung disease (except for those induced by radiation therapies and are asymptomatic).
- 18. Active tuberculosis infection.
- 19. Any active infection requiring systemic anti-infection therapy within 14 days before the first dose of investigational product.
- 20. Subjects who have received prior therapy with an anti-programmed cell death protein-1 monoclonal antibody (anti-PD-1 monoclonal antibody), anti-programmed cell death-ligand 1 monoclonal antibody (anti PD-L1 monoclonal antibody) or anti cytotoxic T-lymphocyte-associated protein 4 monoclonal antibody (anti-CTLA-4 monoclonal antibody).
- 21. Subjects with a known severe allergy to monoclonal antibodies (≥ Grade 3 per CTCAE v 4.03) or uncontrolled allergic asthma.
- 22. Women in pregnancy or lactation.
- 23. Subjects with active alcohol or drug dependence.
- 24. Subjects with uncontrollable concomitant diseases including but not limited to symptomatic congestive heart failure, uncontrolled hypertension, unstable angina, active gastrointestinal ulcer or hemorrhagic disorders.
- 25. Subjects with a history of psychiatric disease; or subjects with incapacity or limited capacity.
- 26. Underlying condition that in the investigator's opinion would increase the risk of investigational product administration or confound the assessment for its toxicity.

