4. STUDY POPULATION

It's planned to enroll approximately 80 subjects with R/R ENKTL in this trial.

The detailed inclusion and exclusion criteria are listed below.

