5.3.2 Criteria for Dose Modification of Investigational Product

Dose increase or reduction of CS1001 is not permitted in this trial. The investigational product will be **withheld** for any of the following investigational drug-related adverse reactions:

- 1. Grade 2 pneumonitis
- 2. Grade 2 or 3 colitis; Grade 3 diarrhea or persistent Grade 2 diarrhea
- 3. Grade 2 hepatitis (elevation of ALT, AST, or total bilirubin levels)
- 4. Grade 2 hypophysitis without adrenal crisis
- 5. Grade 2 nephritis
- 6. Grade 3-4 hypothyroidism
- 7. Grade 3 hyperthyroidism lasting for 6 weeks or more despite proper management
- 8. Grade 3 dermatitis
- 9. Grade 2 neuromuscular toxicity
- 10. Grade 2 ocular toxicity
- 11. Other Grade 2 AEs (for example arthritis, pancreatitis, hemolytic anemia, adrenal insufficiency, myasthenic syndrome, and rhabdomyolysis)
- 12. Grade 4 hematologic toxicity
- 13. Any Grade 3 abnormal laboratory test results except for the following situations:
 - Grade 3 hematologic toxicity.

- Study treatment will be delayed when Grade 2 hepatitis occurs.
- 14. Any AE, abnormal laboratory test result, or intercurrent condition that in the investigator's opinion requires postponing study treatment.

Subjects may resume investigational treatment when the above AE(s) resolve(s) to Grade 0/1 or baseline and the dose of systemic corticosteroid for treating the AE(s) have been tapered to 10 mg daily prednisone equivalents or less.

The investigational treatment will not be resumed for dosing delay due to any cause for more than **9 weeks** (12 weeks after the last dose). (Subject may continue treatment if he/she still benefits clinically at the discretion of investigator in consultation with the sponsor's medical monitor.)

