5.3.3 Criteria for Permanent Discontinuation of Investigational Treatment

The investigational product will be **permanently discontinued** after consultation with the sponsor's medical monitor for any of the following drug-related adverse events:

- Grade 3-4 pneumonitis
- Grade 4 colitis, recurrent Grade 3 colitis, or colitis with symptom suggestive of intestinal perforation
- Grade 3 hepatitis (elevation of ALT, AST, or total bilirubin levels)
- Grade 4 abnormal laboratory test results except for the following situations:

-Grade 4 neutropenia lasting for \leq 5 days

-Grade 4 lymphocytopenia or leukopenia

- Solitary Grade 4 electrolyte disorder/imbalance that can be corrected by electrolyte supplementation/adequate treatment in 72 hours without any clinical consequence.

- Grade 3-4 hypophysitis or adrenal crisis
- Grade 3-4 nephritis
- Grade 4 hyperthyroidism
- Grade 4 dermatitis
- Grade 3-4 neuromuscular toxicity
- Grade 3-4 ocular toxicity
- Other Grade 3-4 AEs (for example arthritis, pancreatitis, hemolytic anemia, adrenal insufficiency, myasthenic syndrome, and rhabdomyolysis) except for Grade 3/4 hypothyroidism
- Grade 4 infusion-related reactions

Permanent discontinuation of investigational product will be considered for recurrence of any of the following Grade ≥ 2 irAEs: pneumonitis, ocular toxicity, cardiac toxicity, and at the discretion of the investigator.

For subjects who meet any of the above criteria although benefiting from investigational treatment, the sponsor's medical monitor and the investigator will discuss and make the final decision in the subject's best interest.

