7.6 LIVER FUNCTION TEST FINDINGS

If ALT or AST > 3 x ULN with elevation in total bilirubin (>2 x ULN), it will be considered as a marker of severe liver injury after ruling out Cholelithiasis or other clinical jaundices that may lead to bilirubin. Therefore, any of the following events must be reported as an AE by the investigator:

- During the course of treatment, ALT or AST > 3 x baseline level; or ALT or AST >2 x baseline level and total bilirubin > 2 x ULN (direct bilirubin 35%) in a subject with baseline transaminase elevation;
- ALT or AST > 3 x baseline level with clinical jaundice during the course of treatment.

The most appropriate diagnosis or clinical test finding (if diagnosis unestablished) will be recorded in the eCRF and reported to the sponsor within 24 hours when the investigator gets aware of it, whether it's an SAE or not.

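### Inclusion criterion 9f joins AST and ALT with *or* in the synopsis and SAP Appendix 1 but with *and* in Protocol Section 4.1; the texts conflict only for a patient with exactly one enzyme above 2.5 × ULN.

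*Protocol*

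**What the plan says.** Criterion 9 lists the organ-function limits for entry, and item f is the transaminase limit.

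- **Protocol synopsis, item 9f:** the ceiling of 2.5 × ULN applies to "Aspartate aminotransferase (AST) or alanine aminotransferase (ALT").
- **Protocol Section 4.1, item 9f:** the same ceiling, with the two enzymes joined by *and*.
- **SAP Appendix 1, item 9f:** the same *or* wording as the synopsis. This appendix reproduces the version 3.0 synopsis, so it is a copy and not separate evidence of intent.

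The synopsis list is headed "Key Inclusion/Exclusion Criteria". Section 4 introduces its own list with "The detailed inclusion and exclusion criteria are listed below". Neither document states which list governs if they differ.

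**The concern.** The threshold is identical in all three places and only the connective differs, but the connective sets the rule. Taken literally, *or* is satisfied as soon as one enzyme is within 2.5 × ULN and places no numeric limit on the other. *And* limits both.

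This is an operative safety limit for a drug whose expected adverse events include hepatitis (Protocol Section 1.2.3). The synopsis reproduces the numbered criteria with their numeric limits, so a site could take it as a working list and accept a patient whom Section 4.1 excludes.

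**Working it through.** No sample size, power or error rate enters this point. The check is a comparison of wording and a four-case table.

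**Inputs.** Let L = 2.5 × ULN, the ceiling in all three texts. Literal synopsis and SAP Appendix 1: eligible if AST ≤ L or ALT ≤ L. Section 4.1: eligible if AST ≤ L and ALT ≤ L.

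| AST | ALT | Synopsis, literal | Section 4.1 | Agree? |
|---|---|---|---|---|
| ≤ L | ≤ L | eligible | eligible | yes |
| > L | ≤ L | eligible | not eligible | no |
| ≤ L | > L | eligible | not eligible | no |
| > L | > L | not eligible | not eligible | yes |

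The rules differ in 2 of the 4 cases, both with exactly one enzyme above L. Examples, in multiples of ULN:

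- AST 2.4, ALT 1.0: eligible under both.
- AST 2.6, ALT 1.0: eligible under the literal synopsis, not under Section 4.1.
- AST 2.6, ALT 2.6: not eligible under either.

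The table also shows that anyone who meets Section 4.1 meets the synopsis. The disagreement runs one way: the synopsis is the looser text.

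**Which reading is intended.** Three features point to *and*.

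1. Section 4 describes its list as the detailed one, while the synopsis offers key criteria.
2. The next item in the same synopsis list, 9g, uses *and* where two tests must both meet a limit: "prothrombin time (PT) and activated partial thromboplastin time (APTT").
3. The on-treatment rules count elevation of either enzyme as hepatitis. Section 5.3.2 withholds drug for "Grade 2 hepatitis (elevation of ALT, AST, or total bilirubin levels"), and Section 5.3.3 discontinues it permanently for "Grade 3 hepatitis (elevation of ALT, AST, or total bilirubin levels"). If one raised enzyme is enough to act on during treatment, the matching entry rule is that both are within the limit.

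**Is either wording superseded?** No. Both are in the current version 3.0 text. The version 3.0 amendment table records changes to the creatinine and bilirubin items of this criterion and none to the transaminase item. That silence is weak evidence about earlier versions, because the table covers major amendments and separately mentions unitemised typographical updates throughout.

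**The case against.** The strongest reply is that the conflict resolves itself. Investigators sign that they have read the full protocol, and Section 10.4.3 tells them to follow all of it. Since Section 4.1 is the stricter text, a patient with one raised enzyme fails the protocol whatever the synopsis says. On this view *or* is loose drafting for *each of*, inside a criterion whose lead-in already requires the absence of liver dysfunction.

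Other safeguards support the reply. Criterion 10 requires toxicity of prior anti-cancer treatment to have recovered to baseline or Grade 1 or lower, with medical-monitor approval needed for irreversible Grade 2. Because criterion 4 requires failure of asparaginase-based therapy, criterion 10 applies to every subject. Exclusion 16 covers active hepatitis B and C. Exclusion 26 covers an underlying condition that the investigator believes "would increase the risk of investigational product administration or confound the assessment for its toxicity", and exclusion 27 covers unsuitability in the investigator's opinion.

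Most of this stands, and it makes the practical risk small. It does not remove the defect. Criterion 10 does not reach enzyme elevation from other causes and allows recovery to baseline as an alternative. Exclusions 26 and 27 rest on judgement. None of these criteria states a second AST or ALT limit, and a numeric limit should not need the reader to infer which of two texts was meant.

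A reader might also draw three stronger conclusions that the documents do not support:

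- **That Section 7.6 shows one raised enzyme is enough to act.** It does not. It is a reporting rule, and its "ALT or AST > 3 x ULN with elevation in total bilirubin" condition is paired with bilirubin above 2 × ULN. Only Sections 5.3.2 and 5.3.3 support the argument about action on treatment.
- **That the synopsis wording decides whether such a subject is an eligibility deviation.** A subject enrolled under version 3.0 must satisfy Section 4.1 in any case.
- **That every enrolled subject with one enzyme above the ceiling should now be recorded as a deviation.** Some subjects may have enrolled under earlier versions, whose item 9f wording is not in the documents.

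**Conclusion.** The inconsistency is real and should be corrected, as a minor point. Two current statements of one numeric entry limit differ by a connective. Read literally, they give opposite answers for a patient with exactly one transaminase above 2.5 × ULN, and the same answer for everyone else. *And* is the likely intention.

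The size in patients cannot be given. The documents report no screening enzyme values, and the number affected may be zero. The conclusion that the texts conflict rests on reading *or* literally; if sites read it as *each of*, nothing differs in practice.

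A reader might infer some effect on the efficacy results, but there is none. The efficacy analysis set depends on dosing and central pathology confirmation, and the safety analysis set on dosing alone. Neither depends on item 9f, so the ORR analysis and its Clopper-Pearson interval are unchanged, as is the sample size. No effect on the SAP's liver-function table can be claimed either, because the SAP does not say whether its rows exclude values already met at baseline.

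**What to change.** Change *or* to *and* in item 9f of the protocol synopsis, and make the same edit in SAP Appendix 1, so that both match Section 4.1: AST and ALT ≤ 2.5 × ULN.

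Optionally, check the screening AST and ALT values already collected. If a subject had one enzyme above 2.5 × ULN, judge eligibility against the protocol version in force at that subject's enrolment. If that makes it a deviation, include it in the SAP's deviation summary and listing only if it is classed as major; neither document classifies a breach of item 9f.

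The cost is one word in each of two documents and, if the option is taken, one pass through existing laboratory data. No new data are needed, and no analysis or table changes.

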1. INTRODUCTION

1.1 DISEASE OVERVIEW

ENKTL is a subtype of mature T cell and NK cell lymphomas. Its incidence varies by geography, higher in Asia than in Europe and North America (22% vs. 5% in mature T cell and NK cell lymphoma, respectively)^[2, 3]. In a multi-center pathology classification survey of 10,002 lymphoma patients in 2012 in China, ENKTL accounted for about 6% of all lymphomas and 28% of all mature T cell and NK cell lymphomas^[4]. Anthracycline-based chemotherapy is not recommended as the high expression of multidrug-resistant p-glycoprotein in ENKTL. Current systemic chemotherapy regimens for ENKTL are asparaginase-based regimens, including SMILE, AspMetDex, and P-Gemox, etc. The ORR and CR of first-line treatment are approximately 80% and 50%, respectively^[5]. High-dose chemotherapy combined with autologous or allogeneic hematopoietic stem cell transplantation is used as consolidation/intensification therapy or second-line salvage therapy but not considered as a standard of care, because of the limited data.

There has not been any large prospective randomized control trial of medical treatment specifically targeting at R/R ENKTL population. A portion of R/R ENKTL patients enrolled in clinical studies for salvage combination chemotherapy have not received asparaginase in the first-line therapy and were treated with the asparaginase-based regime as salvage therapy, who have a better clinical outcome than those who have relapsed or are refractory after receiving asparaginase-based therapy. For now, the salvage combination chemotherapy showed significant toxicity and did not improve the OS significantly, with the median OS being less than 6.4 months^[6-8]. As a targeted therapy, chidamide, a histone deacetylase inhibitor, has also been approved to treat R/R peripheral T-cell lymphoma (including R/R ENKTL) in China. It is reported to have a manageable safety profile and a CR rate of 6.3% (1/16) and an ORR of 18.8% (3/16) in the pivotal phase II trial^[1]. And the post-marketing real-world data showed a CR rate of 6.1% (2/33) and an ORR of 15.2% (5/33)^[9]. Furthermore, a phase II clinical study of anti-CD38 antibody daratumumab in R/R ENKTL reported an ORR of 25% (8/32) and a CR rate of 0%. The median duration of response (DoR) was short (55 days) and the survival benefit was limited (median OS: 130 days)^[10]. In summary, there is a significant unmet medical need for patients with R/R ENKTL.

EBV infection is a primary mechanism and characteristic of ENKTL, which is highly correlated with tumor burden and its response to treatment^[11, 12]. EBV infection induces immune tolerance of ENKTL by upgrading PD-L1 expression in tumor cells^[13, 14]. Around 80% of ENKTL tumor cells express PD-L1^[15]. All of these studies have provided a theoretical foundation for treating ENKTL by inhibiting the PD-1/PD-L1 pathway.

A small retrospective study published in Blood in February 2017 reported the results of pembrolizumab treatment in 7 R/R ENKTL patients after failure of asparaginase-based chemotherapy. Five patients achieved CR (including1 patient had pseudo-progression before achieving CR) and 2 achieved PR. The 5 CR patients were still in remission at a 6-month follow-up, indicating durable response and good tolerability with PD-1/PD-L1 inhibition^[16]. Another retrospective study reported pembrolizumab treatment in 7 R/R ENKTL patients. Two patients achieved CR and 2 patients achieved PR^[17]. A French study was conducted in 13 R/R ENKTL patients failing asparaginase-based chemotherapy. Three patients achieved CR, and 1 achieved PR^[18]. A single-center retrospective study in Korea reported the outcome of 14 R/R ENKTL patients treated with pembrolizumab. Five patients achieved CR and 1 patient achieved PR^[19]. Sintilimab, an anti-PD1 antibody developed in China, was explored in 28 R/R ENKTL patients failing asparaginase-based

regimens in a multicenter, single-arm, phase II trial (ORIENT-4). The CR rate and ORR were 7.1% (2/28) and 53.6% (15/28), respectively. Median DoR was 4.1 months^[8]. Although the data of pembrolizumab in the treatment of R/R ENKTL were from small retrospective case studies, and no anti-PD1 antibody (including pembrolizumab and sintilimab) was approved in the treatment of R/R ENKTL, compared with other drugs, the anti-PD-1 antibody is demonstrated to be an effective treatment with mild adverse effects in R/R ENKTL. All of these data suggest great potential of significant efficacy and better tolerance of anti-PD-1 monoclonal antibody in R/R ENKTL patients who have failed multiple treatment lines.

In summary, R/R ENKTL is a rare disease that lacks effective therapy. Existing clinical data showing the efficacy of anti-PD-1 monoclonal antibody in R/R ENKTL indicate inhibiting the PD-1/PD-L1 pathway to be a potentially effective treatment for R/R ENKTL.

